A serum and urine pregnancy test will be performed for all female subjects of childbearing potential at Screening and Day 1. Additional urine pregnancy tests will be performed every 4 weeks, starting at Day 1 (prior to enrollment) during the treatment period, including at the last treatment period visit and until 4 months after the last study drug dose (or as directed by local RBV label, whichever is more restrictive), as indicated in [Appendix C](#). Determination of postmenopausal status will be made during the Screening period, based on the subject's history.

Females of non-childbearing potential (either postmenopausal or permanently surgically sterile as defined above) at Screening do not require pregnancy testing.

12-Lead Electrocardiogram

A 12-lead resting ECG will be obtained at Screening. The ECG should be performed prior to blood collection.

The ECGs will be evaluated by an appropriately trained physician at the site ("local reader"). The local reader from the site will sign and date all ECG tracings and will provide his/her global interpretation as a written comment on the tracing using the following categories:

- Normal ECG
- Abnormal ECG – not clinically significant
- Abnormal ECG – clinically significant

Only the local reader's evaluation of the ECG will be collected and documented in the subject's source. The automatic machine reading (i.e., machine-generated measurements and interpretation that are automatically printed on the ECG tracing) will not be collected.

Clinical Laboratory Tests

Samples will be obtained at a minimum for the clinical laboratory tests outlined in [Table 10](#) at the visits indicated in [Appendix C](#).

Blood samples for serum chemistry tests should be collected following a minimum 8-hour fast (with the exception of the Screening Visit, which may be non-fasting). Subjects whose visits occur prior to the morning dose of study drug should be instructed to fast after midnight. Subjects whose visits occur following the morning dose of study drug should be instructed to fast after breakfast until the study visit occurs. At the Study Day 1 visit, a fasting blood sample should be collected prior to the first dose of study drug. Blood samples should still be drawn if the subject did not fast for at least 8 hours. Fasting

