CREATININE	1.5 – 1.7 mg/dL	1.8 – 2.0 mg/dL	2.1 – 2.5 mg/dL	>2.5 mg/dL or requires dialysis
GLUCOSE, SERUM, LOW	<LLN – 55 mg/dL <LLN – 3.0 mmol/L	<55 – 40 mg/dL <3.0 – 2.2 mmol/L	<40 – 30 mg/dL <2.2 – 1.7 mmol/L	<30 mg/dL <1.7 mmol/L
GLUCOSE, SERUM, HIGH (Fasting)	>ULN – 160 mg/dL >ULN – 8.9 mmol/L	>160 – 250 mg/dL >8.9 – 13.9 mmol/L	>250 – 500 mg/dL >13.9 – 27.8 mmol/L	>500 mg/dL >27.8 mmol/L or acidosis
MAGNESIUM, SERUM, LOW	<LLN – 1.2 mg/dL <LLN – 0.5 mmol/L	<1.2 – 0.9 mg/dL <0.5 – 0.4 mmol/L	<0.9 – 0.7 mg/dL <0.4 – 0.3 mmol/L	<0.7 mg/dL <0.3 mmol/L
MAGNESIUM, SERUM, HIGH	>ULN – 3.0 mg/dL >ULN – 1.23 mmol/L		>3.0 – 8.0 mg/dL >1.23 – 3.30 mmol/L	>8.0 mg/dL >3.30 mmol/L
PHOSPHATE, SERUM, LOW	<LLN – 2.5 mg/dL <LLN – 0.8 mmol/L	<2.5 – 2.0 mg/dL <0.8 – 0.6 mmol/L	<2.0 – 1.0 mg/dL <0.6 – 0.3 mmol/L	<1.0 mg/dL <0.3 mmol/L
POTASSIUM, SERUM, LOW	<LLN – 3.0 mmol/L		<3.0 – 2.5 mmol/L	<2.5 mmol/L
POTASSIUM, SERUM, HIGH	>ULN – 5.5 mmol/L	>5.5 – 6.0 mmol/L	>6.0 – 7.0 mmol/L	>7.0 mmol/L
PROTEIN, SERUM, LOW	5.5 – 6.0 g/dL	<5.5 – 5.0 g/dL	<5.0 g/dL	
SODIUM, SERUM, LOW	<LLN – 130 mmol/L		<130 – 120 mmol/L	<120 mmol/L
SODIUM, SERUM, HIGH	>ULN – 150 mmol/L	>150 – 155 mmol/L	>155 – 160 mmol/L Hospitalization may be indicated	>160 mmol/L
TRIGLYCERIDES HIGH (fasting)	150-300 mg/dL; 1.71 – 3.42 mmol/L	>300-500 mg/dL; >3.42-5.7 mmol/L	>500-1000 mg/dL; >5.7 – 11.4 mmol/L	>1000 mg/dL; >11.4 mmol/L
URIC ACID, SERUM, HIGH	7.5 – 10.0 mg/dL	10.1-12.0 mg/dL	12.1-15.0 mg/dL	>15.0 mg/dL

Clinical Toxicity Grades for HCV Studies
v1.1; 08 June 2009

Clinical Toxicity Grades for HCV Studies (Continued)				
	GRADE 1 TOXICITY	GRADE 2 TOXICITY	GRADE 3 TOXICITY	GRADE 4 TOXICITY
ENZYMES				
ALT/SGPT	>ULN - 3.0 × ULN	>3.0 - 5.0 × ULN;	>5.0 - 20.0 × ULN	>20.0 × ULN
AST/SGOT	>ULN - 3.0 × ULN	>3.0 - 5.0 × ULN;	>5.0 - 20.0 × ULN	>20.0 × ULN
ALKALINE PHOSPHATASE	>ULN - 2.5 × ULN	>2.5 - 5.0 × ULN	>5.0 - 20.0 × ULN	>20.0 × ULN
AMYLASE	>ULN - 1.5 × ULN	>1.5 - 2.0 × ULN	>2.0 - 5.0 × ULN	>5.0 × ULN
LIPASE	>ULN - 1.5 × ULN	>1.5 - 2.0 × ULN	>2.0 - 5.0 × ULN	>5.0 × ULN

- 1 Adapted from the National Cancer Institute's Common Terminology Criteria for Adverse Events v4.0 (CTCAE)
- 2 Used for all HCV development compounds

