 - Treatment experienced, NS5Ai-experienced only
 - Treatment experienced, PI- and NS5Ai-experienced
 - Treatment experienced, NS5Bi-experienced only
 - Treatment experienced, NS5Bi- and PI-experienced
 - Treatment experienced, NS5Bi- and NS5Ai-experienced
 - Treatment experienced, NS5Bi-, PI- and NS5Ai-experienced
 - HCV mono-infected vs. HCV/HIV-1 co-infected;
 - Cirrhotic vs. non-cirrhotic;
 - Baseline fibrosis stage (equivalent to Metavir F0 – F1, F2, F3, or F4);
 - Baseline HCV RNA level (< 1,000,000, ≥ 1,000,000 to < 2,000,000, ≥ 2,000,000 IU/mL);
 - History of diabetes (yes/no);
 - History of bleeding disorders (yes/no);
 - History of depression or bipolar disorder (yes/no);
 - History of cardiovascular disease (yes/no);
 - Injection drug user (yes, within last 12 months; yes, more than 12 months ago; or no);
 - Use of stable opiate substitution (yes/no);
-

- Tobacco use (current, former, never, or unknown);
- Alcohol use (current, former, never, or unknown);
- Concomitant use of proton pump inhibitors (PPIs) [yes/no];

For subjects with cirrhosis, the following will be summarized:

- Baseline Child-Pugh Score (5, 6, or > 6).

Any concomitant medication coded to the WHO Drug Dictionary ATC code of A02BC will be counted as a PPI.

HOMA-IR is defined as $\text{fasting glucose (mmol/L)} \times \text{fasting insulin } (\mu\text{IU/mL}) \div 22.5$. Subjects who do not have concurrent fasting glucose and fasting insulin values at baseline will be excluded from the summary of baseline HOMA-IR.

Baseline fibrosis stage is defined for subjects with non-missing liver biopsy scores, FibroScan scores, or FibroTest scores. Only one score will be used to categorize each subject even if a subject has more than one score recorded. If a biopsy score is present, then it will be used to categorize the subject, regardless of the FibroScan/FibroTest score. Similarly, if a FibroScan score is present along with a FibroTest score but biopsy score is absent, then the FibroScan score will be used to categorize the subject. If biopsy and FibroScan scores are not present and more than one FibroTest result is available, then the baseline FibroTest result (i.e., last non-missing FibroTest result on or before Day 1) will be used to categorize the subject. Subjects will be categorized as F0 – F1, F2, F3, or F4 according to [Table 7](#).

Table 7. Baseline Fibrosis Stage

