11.4 Analysis of Laboratory Data

Data collected from the central and local laboratories, including additional laboratory testing due to a serious AE, will be used in all analyses.

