11.4.1 Variables and Criteria Defining Abnormality

Hematology variables to be summarized include: hematocrit, hemoglobin, red blood cell (RBC) count, white blood cell (WBC) count, neutrophils, bands, lymphocytes, monocytes, basophils, eosinophils, platelet count, reticulocyte count, prothrombin time (PT), international normalized ratio (INR), and activated partial thromboplastin time (aPTT).

Chemistry variables to be summarized include: blood urea nitrogen (BUN), creatinine, total bilirubin, direct and indirect bilirubin, alanine aminotransferase (ALT), aspartate aminotransferase (AST), alkaline phosphatase, sodium, potassium, calcium, inorganic phosphorus, cholesterol, total protein, glucose, triglycerides, albumin, chloride, bicarbonate, magnesium, total insulin, gamma-glutamyl transferase (GGT), creatinine clearance (calculated using Cockcroft-Gault formula), and eGFR (calculated using MDRD equation).

Urinalysis variables to be summarized include: specific gravity and pH.

The definitions of toxicity grades for laboratory parameters are presented in [Table 11](#).

Table 11. Definitions of Toxicity Grades 1, 2, 3, and 4 for Laboratory Values

Test	Grade 1	Grade 2	Grade 3	Grade 4
ALT	> ULN – 3 × ULN	> 3 – 5 × ULN	> 5 – 20 × ULN	> 20 × ULN
AST	> ULN – 3 × ULN	> 3 – 5 × ULN	> 5 – 20 × ULN	> 20 × ULN
Alkaline Phosphatase	> ULN – 2.5 × ULN	> 2.5 – 5 × ULN	> 5 – 20 × ULN	> 20 × ULN
GGT	> ULN – 2.5 × ULN	> 2.5 – 5 × ULN	> 5 – 20 × ULN	> 20 × ULN
Total Bilirubin	> ULN – 1.5 × ULN	> 1.5 – 3 × ULN	> 3 – 10 × ULN	> 10 × ULN
Hemoglobin	< LLN – 100 g/L	< 100 – 80 g/L	< 80 g/L	--
White blood cells	< LLN – 3.0 × 10 ⁹ /L	< 3.0 – 2.0 × 10 ⁹ /L	< 2.0 – 1.0 × 10 ⁹ /L	< 1.0 × 10 ⁹ /L
Absolute Neutrophil Count	< LLN – 1.5 × 10 ⁹ /L	< 1.5 – 1.0 × 10 ⁹ /L	< 1.0 – 0.5 × 10 ⁹ /L	< 0.5 × 10 ⁹ /L
Platelet count	< LLN – 75.0 × 10 ⁹ /L	< 75.0 – 50.0 × 10 ⁹ /L	< 50.0 – 25.0 × 10 ⁹ /L	< 25.0 × 10 ⁹ /L
INR	> 1 – 1.5 × ULN	> 1.5 – 2.5 × ULN	> 2.5 × ULN	--
Glucose (increased)	> ULN – 8.9 mmol/L	> 8.9 – 13.9 mmol/L	> 13.9 – 27.8 mmol/L	> 27.8 mmol/L
Glucose (decreased)	< LLN – 3.0 mmol/L	< 3.0 – 2.2 mmol/L	< 2.2 – 1.7 mmol/L	< 1.7 mmol/L
Creatinine	> ULN – 1.5 × ULN	> 1.5 – 3 × ULN	> 3 – 6 × ULN	> 6 × ULN
Creatinine clearance	< LLN – 60 mL/min	< 60 – 30 mL/min	< 30 – 15 mL/min	< 15 mL/min
Cholesterol	> ULN – 7.75 mmol/L	> 7.75 – 10.34 mmol/L	> 10.34 – 12.92 mmol/L	> 12.92 mmol/L
Albumin	< LLN – 30 g/L	< 30 – 20 g/L	< 20 g/L	--

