11.4.2 Statistical Methods

The baseline value for clinical laboratory tests will be the last non-missing measurement on or before the day of the first dose of study drug. Values on Day 1 must also be before the time of first dose if time is available. The same baseline value will be used for changes to Treatment Period visits and changes to Post-Treatment Period visits.

Visit Values

For each protocol-specified laboratory parameter, values at each visit (baseline and post-baseline, including applicable post-treatment visits) will be summarized with the sample size, mean, standard deviation, minimum, median, and maximum.

Change from Baseline

For each laboratory parameter listed in Section 11.4.1, changes from baseline to each post-baseline visit, including applicable post-treatment visits, will be summarized with the sample size, baseline mean; visit mean; and change from baseline mean, standard deviation, minimum, median, and maximum.

Shift Tables

Individual changes in the laboratory parameters listed in Section 11.4.1 will be tabulated using shift tables. Laboratory data values will be categorized as low, normal, or high based on normal ranges of the laboratory used for each sample. Shift tables from baseline to minimum value and maximum value during the Treatment Period will be created. For each parameter, the shift tables will cross tabulate the frequency of subjects with baseline values below/within the normal range to maximum above the normal range and with baseline values within/above the normal range to minimum below the normal range.

Maximum Toxicity Grade

The laboratory parameters listed in Table 11 will be assigned a toxicity grade of 1, 2, 3, or 4. The number and percentage of subjects with a maximum toxicity grade of 1, 2, 3

or 4 during the Treatment Period will be tabulated. To be counted, the post-baseline value must have a toxicity grade that is more extreme than the toxicity grade corresponding to the baseline value. For each laboratory parameter in Table 11, the summary will also include the number and percentage of subjects with a post-baseline maximum of at least Grade 3. A listing of all relevant laboratory parameters will be provided for each subject who had an increase to Grade 2 or higher for any laboratory variable in Table 11.

Assessment of Hepatic Laboratory Values

The number and percentage of subjects with laboratory values meeting the following criteria during treatment will be summarized:

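### SAP 11.4.2 grades all glucose values, and summarises change in glucose and insulin, without regard to the fasting status that the protocol records

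*SAP*

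**What the plan says.** **Sampling (Protocol 5.3.1.1, Clinical Laboratory Tests).** The rule is fasting: "Blood samples for serum chemistry tests should be collected following a minimum 8-hour fast (with the exception of the Screening Visit, which may be non-fasting"). Two provisions loosen it. First, "Blood samples should still be drawn if the subject did not fast for at least 8 hours". Second, "Subjects whose visits occur following the morning dose of study drug should be instructed to fast after breakfast until the study visit occurs". The Day 1 sample is to be fasting and taken before the first dose. Fasting or non-fasting status goes into the source documents and onto the laboratory requisition.

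**Values analysed (SAP 6.2 and 11.4).** Central and local results, "including additional laboratory testing due to a serious AE, will be used in all analyses". For graded summaries, several values on one day are not averaged and each is considered.

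**Grading (SAP 11.4.1 and 11.4.2).** "The laboratory parameters listed in Table 11 will be assigned a toxicity grade of 1, 2, 3, or 4". Table 11 grades raised glucose as Grade 1 from the ULN to 8.9 mmol/L, Grade 2 above 8.9 to 13.9, Grade 3 above 13.9 to 27.8, and Grade 4 above 27.8. The row has no fasting qualifier. The summary takes the maximum grade in the Treatment Period and counts it only when it is worse than the baseline grade. An increase to Grade 2 or higher also triggers a listing.

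**The one place where fasting status is used (SAP 7.1).** "Subjects who do not have concurrent fasting glucose and fasting insulin values at baseline will be excluded from the summary of baseline HOMA-IR".

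**The concern.** Glucose and insulin depend on when the subject last ate. If baseline is fasting and some later samples are not, the two are not like for like. The counting rule then works in one direction: a post-meal rise can move a subject into a worse grade, and a maximum over several visits needs only one such value. The SAP asks for two consecutive values to confirm a post-nadir ALT rise above 5 × ULN, but asks for no confirmation of glucose.

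The outputs at stake are the raised-glucose rows of the maximum-grade table, the Grade 2 or higher listing, and the mean changes in glucose and total insulin. There is no control group to show how many such grades would arise from meals alone. Safety is part of the primary objective, and with about 50 subjects one subject is 1/50 = 2 percentage points.

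**Working it through.** **1. Can non-fasting samples reach the graded table?** Yes, by three routes:
- a missed fast, where the sample is still drawn;
- a visit after the morning dose, where the fast runs only from breakfast and can be shorter than 8 hours (Protocol 5.3.1.2 has every dose taken with food);
- local or SAE-related samples, which SAP 11.4 admits and whose fasting status may be unknown.

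No fasting filter appears in SAP 6.2, 11.4, 11.4.1 or 11.4.2.

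**2. Is the comparison symmetric?** No. Day 1 is meant to be fasting, while later samples are fasting by rule but with the exceptions above. With the worse-than-baseline rule, this tends to add counts. There is one route the other way. If Day 1 glucose is missing, the last earlier value becomes baseline, and Screening may be non-fasting, so a real rise could be hidden.

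**3. Where do the cut-points come from?** The toxicity table that the amendment deleted from the protocol (Appendix E) listed high glucose at 160, 250 and 500 mg/dL in a row labelled fasting. Dividing by 18.016 gives 8.88, 13.88 and 27.75 mmol/L, which match Table 11's 8.9, 13.9 and 27.8 after rounding. This shows a likely origin only, because the appendix is superseded.

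**4. How large could the effect be?** The documents give neither the non-fasting rate nor the distribution of post-meal glucose. For illustration, let f be the share of on-treatment samples that are non-fasting. Let g be the chance that such a sample exceeds 8.9 mmol/L in a subject whose baseline grade is lower. Both are assumptions, and visits are treated as independent. From the documents: Arm A about 5 subjects with 4 on-treatment chemistry visits, Arm B about 45 subjects with 5.

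Expected subjects counted at Grade 2 or higher = 5 × [1 − (1 − fg)^4] + 45 × [1 − (1 − fg)^5]

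| f (assumed) | g (assumed) | fg | Arm A | Arm B | Total of 50 |
|---|---|---|---|---|---|
| 5% | 2% | 0.001 | 0.02 | 0.22 | 0.24 (0.5%) |
| 10% | 5% | 0.005 | 0.10 | 1.11 | 1.21 (2.4%) |
| 20% | 5% | 0.010 | 0.20 | 2.21 | 2.40 (4.8%) |
| 30% | 10% | 0.030 | 0.57 | 6.36 | 6.93 (13.9%) |

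Grade 1 counts are not included, since the ULN is not given.

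**5. Total insulin.** Protocol Appendix C samples it only at Day 1 and at EOT or premature discontinuation, and Table 11 does not grade it. Only one change from baseline is affected, so the 4- or 5-visit formula does not apply to it.

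**The case against.** The strongest reply is that fasting is the protocol's default at every visit after Screening, not only on Day 1, so the issue is confined to exceptions whose frequency nobody has stated. That is right, and it limits the point.

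Second, using every value is a defensible, inclusive convention for safety data, and the Grade 2 or higher listing already allows review subject by subject. This also stands. It is why non-fasting values should not simply be dropped: doing so would remove non-fasting values between 8.9 and 13.9 mmol/L from view. But the plan does not ask for fasting status in that listing, so a reader could not separate the two kinds of value.

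Third, the HOMA-IR restriction follows from that index's definition and does not prove that a grading rule was forgotten. Agreed. It shows only that the analysis presupposes fasting status at baseline.

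Fourth, subjects with diabetes do not clearly enlarge the problem. One whose fasting baseline is already raised carries a grade and needs a larger rise to be counted.

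A reader might also infer three stronger claims that the documents do not support:
- **That a third to four-fifths of subjects are affected.** With an assumed 10–30% non-fasting rate q, 1 − (1 − q)^k gives 34–76% for k = 4 and 41–83% for k = 5. That is the chance of having any non-fasting sample, not of receiving a false grade.
- **That Table 11 contradicts its own fasting definition.** The fasting label exists only in the deleted appendix, and Table 11 is not a copy of it: INR and creatinine, for example, are graded differently. The point rests on baseline and later values not being comparable, and needs no label.
- **That meals will appear as Grade 3 hyperglycemia or as adverse events.** Grade 3 needs a value above 13.9 mmol/L, and nothing in the documents shows how often a meal would produce one. Table 11 gives laboratory grades. Treatment-emergent is the SAP's term for adverse events, and Protocol 6.1.1.1 does not usually count laboratory abnormalities as such.

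**Conclusion.** The point holds as a minor gap in a descriptive safety analysis. Samples that may follow a meal enter the glucose grades and the glucose and insulin change summaries with no account of fasting status, although that status is recorded. The likely effect is some extra worsened laboratory glucose grades, mainly Grade 1 or 2.

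Its size cannot be derived from the documents. The range of about 0.2 to 6.9 of 50 subjects depends entirely on the assumed f and g and on independence between visits, and at its low end it is less than one subject. SVR12, its confidence intervals and the sample size do not change.

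**What to change.** In SAP 11.4.1 and 11.4.2:
- Keep the all-values table as planned.
- Beside it, present the maximum raised-glucose grade from samples recorded as fasting, at baseline and post-baseline alike.
- Show non-fasting and unknown-status samples in a separate row, and flag fasting status in the Grade 2 or higher listing, so that no marked elevation is lost.
- State how a subject is handled in the fasting summary when the only pre-dose glucose is a non-fasting Screening value.
- Restrict change from baseline to fasting pairs, both for glucose and for total insulin (Day 1 to EOT or premature discontinuation).

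The cost is a footnote, a filter and one extra display, with no change to study conduct. The recorded status may need to be transferred from the requisition if post-baseline flags are not yet in the analysis data. There will be slightly fewer evaluable pairs. Local or SAE-related samples may lack the flag, and these go in the unknown row.

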6.1.2 Study Days

Study Days (Days Relative to the First Dose of Study Drug)

Study days are calculated for each time point relative to the first dose of study drug. Study days are negative values when the time point of interest is prior to the first study drug dose day. Study days are positive values when the time point of interest is after the first study drug dose day. There is no Study Day 0. Study Day 1 is the day of the first dose of study drug.

Study Drug End Days (Days Relative to the Last Dose of Study Drug)

Study drug end days are calculated for each time point relative to the last dose of study drug. The last day of study drug dosing is defined as Study Drug End Day 0. Days before it have negative study drug end days and days after it have positive study drug end days.

Final Treatment Value

The final treatment value is defined as the last non-missing measurement collected after Study Day 1 and on or before Study Drug End Day 2.

Final Post-Treatment Value

The final post-treatment value for each subject is the last non-missing measurement collected after Study Drug End Day 2 and on or before Study Drug End Day 999.

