Note: For all windows, data must be on or before Study Drug End Day 2. The result closest to the scheduled time point will be used. Child-Pugh scores are only collected for subjects with compensated cirrhosis at the Screening Visit and End of Treatment Visit (Week 12 Visit for Arm A and Week 16 Visit for Arm B, or Premature Discontinuation Visit).

Table 5. Analysis Time Windows for HCV RNA and Resistance Endpoints (Post-Treatment Period)

Scheduled Visit ^a	Nominal Day (Study Drug End Day)	Time Window (Study Drug End Day Range)
Post-Treatment Week 4	28	3 to 56
Post-Treatment Week 12	84	57 to 126
Post-Treatment Week 24	168	127 to 999
SVR ₄ ^b	28	3 to 56
SVR ₁₂ ^b	84	57 to 126
SVR ₂₄ ^b	168	127 to 210

a. Post-Treatment Visits are applicable for subjects who received at least one dose of study drug.

b. For SVR windows, the last value in the window will be used.

Note: The result closest to the scheduled time point will be used, except for SVR₄, SVR₁₂, and SVR₂₄. For all windows, data must occur after Study Drug End Day 2. Study Drug End Day 0 is defined as the day of the last dose of study drug.

Table 6. Analysis Time Windows for Safety Laboratory and Vital Sign Measurements and Child-Pugh Score (Post-Treatment Period)

Scheduled Time ^a	Nominal Day (Study Drug End Day)	Time Window (Study Drug End Days Range)
Post-Treatment Week 4	28	3 to 56
Post-Treatment Week 12	84	57 to 126
Post-Treatment Week 24	168	127 to 999
Final Post-Treatment Visit ^a	> 2 days after last dose of study drug	

a. Post-Treatment Visits are applicable to subjects who received at least one dose of study drug.

b. The last value within the Post-Treatment Period window will be used to define the Final Post-Treatment value. The lower bound of this Final window is Study Drug End Day 3. Study Drug End Day 0 is defined as the day of the last dose of study drug.

Note: The result closest to the scheduled time point will be used. For all windows, data must occur after Study Drug End Day 2. Vital signs are collected at Post-Treatment Week 4 only; hematology, chemistry, urinalysis, and coagulation panels are collected at Post-Treatment Week 4 Visit or at Post-Treatment Discontinuation Visit if subject discontinues during the Post-Treatment Week 4 window. Child-Pugh scores are only collected for subjects with compensated cirrhosis at Post-Treatment Weeks 12, 24, and the Premature Discontinuation Visit.

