For the **assessments of hepatic laboratory values** and **hepatic laboratory abnormalities of potential interest**, the maximum ratio relative to the ULN will be used to determine if subjects meet any of the criteria listed above. The ALT and total bilirubin values do not need to be concurrent in order to meet the defined criteria in statistical summaries. For ALT, the post-baseline value must represent an increase from the first nadir (including baseline) to be counted. First nadir is defined as the last value prior to the first increase. For total bilirubin, a subject will be counted if the post-baseline laboratory value meets the above criteria regardless of the baseline laboratory value (i.e., the post-baseline laboratory value does not need to be worse than the baseline laboratory value), except where noted above. A confirmed post-nadir increase in ALT is defined as two consecutive values of $ALT > 5 \times ULN$ after nadir, either both during treatment or at the final treatment measurement and the next consecutive post-treatment measurement. A single post-nadir ALT value of greater than $5 \times ULN$ followed by lost to follow-up (no additional ALT values) also will be considered (i.e., will not require confirmation). The ratio of direct to total bilirubin will be calculated using the same date/time sample corresponding to the total bilirubin elevation.

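### SAP 11.4.2: the hepatic counts stop at the end of treatment, so a bilirubin rise just after stopping drug leaves the subject in the lower ALT/bilirubin row; a supplementary column through Post-Treatment Week 4 would be a cheap improvement

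*SAP*

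**What the plan says.** SAP 11.4.2, under Assessment of Hepatic Laboratory Values, sets four criteria: post-nadir ALT above 5 × ULN; bilirubin at least 2 × ULN and above baseline; and post-nadir ALT above 3 × ULN, split by whether bilirubin is above 2 × ULN or not. The lead-in is "The number and percentage of subjects with laboratory values meeting the following criteria during treatment will be summarized". The two abnormalities of interest that follow (confirmed ALT above 5 × ULN; ALT above 3 with bilirubin above 2 × ULN and a direct/total ratio above 0.4) are drawn from the same events, so they inherit the period.

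The period is bounded elsewhere in the SAP. The note to Table 4, which covers safety laboratory data in the Treatment Period, says "For all windows, data must be on or before Study Drug End Day 2". The final treatment value in SAP 6.1.2 is "the last non-missing measurement collected after Study Day 1 and on or before Study Drug End Day 2". Protocol 1.3 ends the Treatment Period at the last dose.

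Three rules in 11.4.2 govern classification:

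- each subject is classified by the highest multiple of ULN reached;
- on timing, "The ALT and total bilirubin values do not need to be concurrent in order to meet the defined criteria in statistical summaries";
- an ALT value counts only if it has risen from the subject's first nadir, and baseline can serve as that nadir.

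The only reach past treatment is the confirmation of ALT above 5 × ULN, where the two values may be "either both during treatment or at the final treatment measurement and the next consecutive post-treatment measurement". Bilirubin has no such allowance.

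**The concern.** ALT and bilirubin need not coincide, so a bilirubin rise later in treatment moves a subject into the higher combined row. Only the period cut-off keeps a rise after stopping drug from doing the same.

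The protocol makes that sequence plausible. For confirmed ALT of at least 5 × ULN and at least twice baseline, section 6.1.7.5 calls for repeat liver tests within a week and further tests until resolution. It stops study drug for rising direct bilirubin, among other triggers. If drug is stopped while bilirubin is rising but still at or below 2 × ULN, the counting window closes two days later, while the protocol is asking for more samples.

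Safety is part of the primary objective, and the combined ALT and bilirubin rows are where a reader looks for possible liver injury. SAP 11.2.1 counts treatment-emergent adverse events to 30 days after the last dose, so the hepatic counts cover a shorter period than the adverse-event tables beside them.

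**Working it through.** The plan gives no figure to reproduce. The check applies the SAP's rules to an assumed Arm B subject and moves the cut-off. All laboratory values are illustrative.

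**Inputs from the documents.** First nadir is the last value before the first increase; the maximum ratio to ULN is used; values need not be concurrent (SAP 11.4.2). Treatment ends at Study Drug End Day 0 (protocol 1.3) or Day 2 (SAP Table 4 note). The Post-Treatment Week 4 laboratory window is Days 3 to 56, nominal Day 28 (SAP Table 6). Planned N is about 50 (SAP 4.2), and safety is summarized overall only (SAP 11.1).

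**Assumed subject, × ULN.** ALT is 2.0, 0.8, 0.7, 0.7, 0.9 and 3.6 at baseline and Weeks 2, 4, 8, 12 and 16, then 4.2 at Post-Treatment Week 4. Bilirubin is 0.6 at baseline, at most 1.4 on treatment, and 2.6 at Post-Treatment Week 4 (Day 28).

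**Step 1: nadir.** The first increase is 0.7 to 0.9, from Week 8 to Week 12, so the first nadir is 0.7. Post-nadir ALT on treatment peaks at 3.6, which is above 3.

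**Step 2: classify by cut-off.**

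| Cut-off (Study Drug End Day) | Max post-nadir ALT | Max bilirubin | ALT > 3, bilirubin ≤ 2 | ALT > 3, bilirubin > 2 | Bilirubin ≥ 2 |
|---|---|---|---|---|---|
| 0 or 2 | 3.6 | 1.4 | counted | no | no |
| 30 | 4.2 | 2.6 | no | counted | counted |
| 56 | 4.2 | 2.6 | no | counted | counted |

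If the direct/total ratio at the late sample were above 0.4, the subject would also enter that abnormality-of-interest row under the Day 30 and Day 56 cut-offs.

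**Step 3: choose the upper bound.** The Week 4 window holds 56 − 3 + 1 = 54 days. A Day 30 cut covers 30 − 3 + 1 = 28 of them and misses 56 − 31 + 1 = 26. With the Week 4 sample on Day 35, the Day 30 cut gives the same result as Day 2, and only the Day 56 cut captures the rise.

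**Step 4: contrasts.**

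- A bilirubin rise within treatment is already captured, because concurrency is not required.
- ALT falling throughout from 9 × ULN (9, 5, 3.5, 2, 1, 0.8, 0.7), with a late bilirubin of 2.5, enters no ALT row under any cut.
- A subject normal on drug, with ALT 6.0 and bilirubin 1.2 at Post-Treatment Week 4, is in no hepatic row at Day 2. With the Week 4 sample included, the subject is in two (ALT > 5; ALT > 3 with bilirubin ≤ 2).

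**Step 5: size.** One subject is 1/50 = 2.0 percentage points of a row.

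**The case against.** The strongest reply is that nothing is wrong with the table. Protocol 8.1.5.2 asks for laboratory abnormalities during treatment, and the SAP's shift tables, maximum grades and vital-sign criteria follow the same convention. A subject whose bilirubin stayed at or below 2 × ULN on treatment is correctly placed in a row that claims no more. This stands: a reader might infer a misclassification or a departure from the protocol, and the documents support neither.

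A reader might also infer that the late rise is hidden, or that listing and count contradict each other. Neither is established. SAP 11.4.2 lists all hepatic values for every subject meeting a criterion, but does not say whether post-treatment values are printed. If they are, a reviewer of about 50 subjects can see the rise. If they are not, the listing does not conflict with the count.

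Nor does a subject who first crosses a threshold after treatment vanish from the safety outputs. Such a subject may appear as an adverse event (protocol 6.1.1.1; SAP 11.2.1), as a hepatic event of special interest (SAP 11.2.3), or in the Post-Treatment Week 4 visit maximum. The subject may also appear in the Grade 3 count or Grade 2+ listing, whose wording leaves the period open. None of these, however, supplies a combined ALT/bilirubin count.

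Two further objections concern the remedy. Day 56 still differs from the adverse-event window, and it lies well beyond exposure, given half-lives of 6 to 9 hours for ABT-493 and 12 to 17 hours for ABT-530 (protocol 3.0). Both are true. They are reasons to label the column supplementary and show HCV RNA status, not to leave already scheduled samples out of every hepatic count.

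**Conclusion.** The point holds as a low-severity improvement. Under the SAP's rules, a subject with post-nadir on-treatment ALT above 3 × ULN and bilirubin first above 2 × ULN after Study Drug End Day 2 is in the lower combined row and in no count of ALT with bilirubin above 2 × ULN. If ALT also passed 5 × ULN on treatment, the subject is in that row too. Ending treatment at the last dose instead of Day 2 gives the same result.

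The frequency cannot be estimated from the documents. No test, interval or SVR12 result is affected. The conclusion rests on reading the hepatic counts as bounded by the Table 4 windows. Section 11.4.2 does not repeat that bound, but it would be too strong to call the period undefined.

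**What to change.** In SAP 11.4.2, keep the on-treatment table. Add one supplementary column that applies the four hepatic criteria and the two abnormalities of interest to all post-baseline values through the Post-Treatment Week 4 window (Study Drug End Day 56), including unscheduled and local results. Provide matching listings that print post-treatment values and HCV RNA status. Say how the confirmed ALT row treats a Week 4 value with no later ALT.

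Two clarifications could go in with the same edit: restate the Day 2 bound in 11.4.2, and give the period for the Grade 3 count and the Grade 2+ listing.

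The cost is SAP wording and a little programming. No new data are needed: protocol Appendix C schedules the Week 4 chemistry for all subjects (for those without cirrhosis it is the last scheduled panel), and SAP 11.4 already admits central and local results. The downside is that some late ALT rises may reflect relapse rather than drug, which the HCV RNA column helps to separate.
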